At the discretion of the investigator, the screening visit may be divided into 2 visits if the visit length is deemed to be too burdensome for the patient. Patients may be rescreened 1 time if there is a change in the patient's medical background, a modification of study entry criteria, or other relevant change. (Note: Details of rescreening must be approved and documented by the medical monitor and/or Clinical Surveillance and Training team.) For patients from Study TV50717-CNS-30046 or Study TV50717-CNS-30060:

The screening evaluation for this open label study occurs at the end of the treatment period in the double-blind study. To reduce patient burden and not collect duplicate information, after obtaining informed consent/assent, depending on the child's age, as appropriate, relevant data collected in Study TV50717-CNS-30046 or Study TV50717-CNS-30060 will be used to provide corresponding data in this open-label study (see [Table 1](#)).

YGTSS Rater Certification: All investigators and subinvestigators who will be administering the YGTSS from screening through the end of study visit must undergo and pass a Rater Certification Program which will be provided separately from this protocol. Every effort must be made to ensure that the same certified rater administers the YGTSS to a specific patient at all visits where this scale is administered, especially at day 1 and at weeks 28, 30, and 54/early termination visits. However, if due to unforeseen circumstances the same rater is absolutely unavailable to complete a visit rating, the YGTSS can be administered only by another certified individual from that study site.

Part A:

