2.2. Study Objectives

2.2.1. Primary Objective

The primary objective of this study is to evaluate the safety and tolerability of long-term therapy with TEV-50717.

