3.1.3. Titration Period (7 Weeks)

As patients from Study SD-809-C-17 will have been off IMP for several months at the time of enrollment, and since patients from Study TV50717-CNS-30046 or Study TV50717-CNS-30060 will have discontinued IMP (TEV-50717 or placebo) for at least 1 week at completion of the parent study, all patients will undergo TEV-50717 dose titration in this study. Patients will receive 6 mg of TEV-50717 with food on the evening of day 1. Tablets should be taken with food (eg, a snack) and should not be taken on an empty stomach. The titration scheme and maximum dose will be determined by body weight and CYP2D6 impairment status from the parent study. Patients will be classified as CYP2D6 impaired if they are receiving a strong CYP2D6 inhibitor or are a CYP2D6 poor metabolizer based on blinded assessment of CYP2D6 genotype at baseline of the parent study. Patients who are CYP2D6 impaired will have a dose cap in the open-label study, as shown in [Table 2](#). Patients and their caregiver/adult will interact weekly with the clinical research staff, either by telephone contact or in-clinic visits from week 1

through week 7 of the titration period, in order to evaluate safety and establish a dose of TEV-50717 that optimally reduces tics and is well tolerated (optimal dose). Safety evaluations during the titration period include assessment of vital signs, monitoring for adverse events and concomitant medications, 12-lead ECGs, and rating scales for depression and suicidality.

In-person (in-clinic) study visits will be scheduled at weeks 2, 4, and 6, and telephone contacts will be scheduled for weeks 1, 3, 5, and 7 in order to assess adverse events and tic severity.

The dose of the IMP should be increased on a weekly basis until one of the following occurs:

- The investigator determines that there has been a clinically meaningful reduction in tics.
- The patient experiences a protocol-defined “clinically significant” adverse event (defined as an adverse event that is related to IMP and is either moderate or severe in intensity or meets the criteria for a serious adverse event).
- The maximum allowable dose is reached, based on the patient’s weight and use of strong CYP2D6 impairment status.

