^a Full screening visit is required for patients who previously completed Study SD-809-C-17. This visit is not required for patients who completed Study TV50717-CNS-30046 or Study TV50717-CNS-30060.

^b Assessment to occur at the end of study week (±3 days).

^c For patients rolling over from Study TV50717-CNS-30046 or Study TV50717-CNS-30060, the week 13 visit (Study TV50717-CNS-30046) or the week 9 visit (Study TV50717-CNS-30060) will be the day 1 visit for Study TV50717-CNS-30047, and patients will continue to enter dosing times in the diary through completion of Study TV50717-CNS-30047. Patients rolling over from Study SD-809-C-17 will need to undergo all day 1 assessments. Study TV50717-CNS-30047 day 1 assessments that are identical to Study TV50717-CNS-30046 week 13 or Study TV50717-CNS-30060 week 9 visit assessments do not need to be repeated.

^d The screening visit may be conducted over 2 separate visits at the discretion of the investigator.

^e Dose adjustment will be made by the investigator after telephone contact with the patient and caregiver/adult to evaluate tic reduction and adverse events (Table 2).

^f For patients enrolled from Study TV50717-CNS-30046 or Study TV50717-CNS-30060, informed consent/assent, depending on the child's age, as appropriate, may be obtained up to 4 weeks in advance.

^g For patients rolling over from Study TV50717-CNS-30046 or Study TV50717-CNS-30060, these data will be obtained from the screening visit of the parent study.

^h Weight must be measured with shoes and outerwear off. Before pulse and BP are measured, the patient must be in a supine or semi erect/seated position and resting for at least 5 minutes (the same position and arm should be used each time vital signs are measured for a given patient).

ⁱ Orthostatic BP and pulse will be measured after patient is in a standing position for at least 3 minutes.

Clinical Study Protocol with Amendment 04

- j For patients rolling over from Study TV50717-CNS-30046, these data will be obtained from the week 12 visit of the parent study. For patients rolling over from Study TV50717-CNS-30060, these data will be obtained from the week 8 visit of the parent study.
- k All ECGs will be performed after at least 5 minutes rest in a supine or semi-supine position.

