- l For patients with clinically significant laboratory abnormalities at week 12 in Study TV50717-CNS-30046, the week 13 value will serve as the day 1 in this study. For patients with clinically significant laboratory abnormalities at week 8 in Study TV50717-CNS-30060, the week 9 value will serve as the day 1 in this study. Rollover for such patients must be approved by the medical monitor and may be delayed.
- m Genotype data will be obtained from the relevant parent study. For the patients rolling over from Study SD-809-C-17, these data will come from the CSR and will be communicated to the relevant investigator.
- n For females who are postmenarchal or ≥ 12 years of age, a urine test will be administered on day 1 and weeks 4, 8, 15, 28, and 34. A serum test will be administered at screening, week 54, and if clinically indicated.
- o MINI Kid modules to be used are as follows: Major Depressive Episode (Module A), (Hypo) Manic Episode (Module D), OCD (Module J), Alcohol Dependence/Abuse (Module L), Substance Dependence/Abuse (Non-alcohol; Module M), ADHD (Module O), Conduct Disorder (Module P), and Psychotic Disorders and Mood Disorders with Psychotic Features (Module R).
- p For children 13 years of age and under, interviews may be performed separately or jointly with the caregiver/adult as appropriate or defined by the scale. For children over 13 years of age, caregiver/adult involvement is strongly encouraged. Questions should be directed to the child, but the caregiver/adult should be encouraged to add relevant information.
- q Children 6 years of age at day 1 will not complete the Self-Report version; the caregiver/adult will complete the Parent version.
- r For patients rolling over from Study TV50717-CNS-30046, these data will be obtained from the week 13 visit of the parent study. For patients rolling over from Study TV50717-CNS-30060, these data will be obtained from the week 9 visit of the parent study.
- s Input from the caregiver/adult is required.
- t The YGTSS, TS-CGI, TS-PGII, and [REDACTED] questionnaires should be performed before any blood draws or ECG assessments.
- u Perform assessment of “Severity Ratings” of the questionnaire. Inventory portions (ie, “Motor Tic Symptom Checklist” and “Phonic Tic Symptom Checklist”) do not need to be performed.

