9.7.1. Safety Endpoints

The following safety endpoints will be assessed in Part A (Day 1, Titration, and Maintenance):

- incidence of adverse events
- observed values and changes from day 1 in vital signs
- observed values and changes from day 1 in the CDI-2 (Parent and Self-Report Profiles)
- observed values in the C-SSRS
- observed values in electrocardiogram (ECG) parameters and shifts from parent study baseline (for patients rolling over from Study TV50717-CNS-30046 or Study TV50717-CNS-30060) or from day 1 (for patient[s] rolling over from Study SD-809-C-17) for clinically significant abnormal findings

- observed values and changes from day 1 in clinical laboratory parameters (hematology, serum chemistry, and urinalysis)

The following safety endpoint will be assessed in Part B (Blinded, Randomized Drug Withdrawal Period and Titration Post-Drug Withdrawal Period):

- incidence of adverse events

In addition to routine monitoring of adverse events, clinical laboratory parameters, 12-lead ECGs, and safety scales, an IDMC will monitor safety during the conduct of the study.

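### Laboratory change from day 1 starts from an on-drug value for most former active-arm rollovers and from a drug-free value for former placebo rollovers

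*Protocol*

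**What the plan says.** The laboratory endpoint in Sections 2.3.1 and 9.7.1 is "observed values and changes from day 1 in clinical laboratory parameters (hematology, serum chemistry, and urinalysis"). It serves the objective in Section 2.2.1: "The primary objective of this study is to evaluate the safety and tolerability of long-term therapy with TEV-50717".

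In Table 1 (Section 3.13) the Day 1 cell for chemistry, hematology and urinalysis carries footnotes j and l.

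- **Footnote j** names the source for the two large parent studies: "For patients rolling over from Study TV50717-CNS-30046, these data will be obtained from the week 12 visit of the parent study" and "For patients rolling over from Study TV50717-CNS-30060, these data will be obtained from the week 8 visit of the parent study".
- **Footnote l** makes an exception. Where the week 12 result was clinically significantly abnormal, "the week 13 value will serve as the day 1 in this study"; for Study TV50717-CNS-30060 the corresponding visits are weeks 8 and 9. Section 3.1.2 repeats the rule.

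On timing, Section 3.1.1 says of these rollovers: "The screening evaluation for this open label study occurs at the end of the treatment period in the double-blind study". The day 1 visit itself is parent week 13 or week 9, and Section 3.1.3 says that by then patients "will have discontinued IMP (TEV-50717 or placebo) for at least 1 week at completion of the parent study".

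For ECG in the same patients, Section 9.7.1 uses another reference: "shifts from parent study baseline (for patients rolling over from Study TV50717-CNS-30046 or Study TV50717-CNS-30060"). Sections 3.3 and 3.13.2 list laboratory tests at day 1 and do not mention the footnote j substitution.

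**The concern.** A change-from-baseline summary of long-term safety is easiest to read when the baseline is the same kind of measurement in every patient, ideally untreated. Here one label, day 1, covers three kinds of value: end of active treatment, end of placebo, and one week after stopping. These are pooled into one mean change.

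Two consequences follow. First, a laboratory effect that developed during the parent study is already in the reference of former active-arm patients, so it cannot show as change in them. Second, footnote l chooses the reference according to the laboratory result, which is the quantity being summarized. The protocol avoids both problems for ECG by going back to the parent-study baseline, and it gives no reason for treating laboratory data differently.

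**Working it through.** **1. Is there a default day 1 blood draw?** Table 4 (Section 5.6) allows 10 mL per sample and 30 to 40 mL in total for rollovers from -30046 and -30060. Their scheduled on-study draws are weeks 8, 28 and 54.

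- Without a day 1 draw: 3 × 10 = 30 mL.
- With a day 1 (week 13 or 9) draw: 4 × 10 = 40 mL.
- SD-809-C-17 rollover: screening, day 1 and weeks 8, 28 and 54 = 5 × 10 = 50 mL, the lower end of the stated 50 to 60 mL.

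The stated range is reproduced. Its 30 mL minimum fits only if no day 1 sample is drawn by default, which supports reading footnote j as the operative rule despite the day 1 listings in Sections 3.3 and 3.13.2.

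**2. Which value does each group carry as day 1?**

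| Group | Source of day 1 laboratory value | State |
|---|---|---|
| Former active arm, no clinically significant abnormality at week 12/8 | Week 12/8 | On drug |
| Former placebo arm, no such abnormality | Week 12/8 | Drug-free |
| Either arm, clinically significant abnormality at week 12/8 | Week 13/9 | After at least 1 week off IMP |
| SD-809-C-17 (about 1 patient) | Own day 1 sample | Several months off IMP |

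**3. How many patients?** Planned enrollment is 1 + 99 + 127 = 227, so the footnote j and l rule governs up to 99 + 127 = 226. The parent allocation ratio is not in the protocol. Let p be the share of these who had active drug:

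- p = 1/3: 226/3 ≈ 75
- p = 1/2: 226/2 = 113
- p = 2/3: 226 × 2/3 ≈ 151

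Those switched by footnote l must be subtracted from each count. Their number is not stated.

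**4. How much dilution?** Let E be the true mean change from the untreated state under long-term therapy, and f the fraction of E already present at week 12/8 in former active patients. Assume the same E in both groups and ignore footnote l switches. Former active patients then show (1 − f)E and former placebo patients show E, so

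pooled change = p(1 − f)E + (1 − p)E = (1 − pf)E.

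With a full plateau by week 12/8 (f = 1) this is (1 − p)E:

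- p = 1/3: 67% of E
- p = 1/2: 50% of E
- p = 2/3: 33% of E

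With no effect yet present (f = 0) the pooled change shows all of E. The protocol gives neither p nor f, so these figures are an illustration under assumption.

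**The case against.** The strongest reply is that change from the start of an extension is a legitimate description of that extension. Part A is descriptive, with no hypothesis tests (Sections 9.1 and 9.5). Observed laboratory values are summarized too, and do not depend on the reference. A result judged clinically significant is recorded as an adverse event whatever the baseline (Section 7.5). The one completed study in Tourette syndrome, with 23 patients treated for up to 8 weeks, showed no clinically meaningful trend in mean laboratory change (Section 1.3.2.2), so no signal is known to be hidden. All of this stands and limits what is at stake. It does not answer the main point: the value labeled day 1 is, by default, not taken at the start of the extension, and its meaning differs by parent-study arm.

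A reader might also infer more than the documents support:

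- **That every patient who had active drug has an on-drug reference.** Footnote l takes out those with a clinically significant abnormality, and the SD-809-C-17 rollover has a fresh day 1 sample.
- **That 226 of 227 patients are biased.** They are subject to the rule. Former placebo patients still have a drug-free reference.
- **That laboratory shift tables are distorted.** The protocol specifies shifts for ECG; for laboratory data it specifies observed values and changes.
- **That footnote l adds regression to the mean toward no effect.** That direction is not established. For elevated values, replacing extremes by a later off-drug result would tend to lower the baseline and enlarge later change. The sound objection is that the reference depends on the outcome.
- **That vital signs, CDI-2 and TTS share the fault.** Footnote j is not on their day 1 cells. Vital signs are taken at day 1, and CDI-2 and YGTSS come from week 13/9, after washout.

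**Conclusion.** The concern holds for laboratory data in -30046 and -30060 rollovers. For former active-arm patients, except those switched by footnote l, change from day 1 is measured from an on-drug value; for former placebo patients it is measured from a drug-free one. Any laboratory effect present by week 12/8 is missing from the change in the first group and diluted in the pooled mean.

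The range of about 67% down to 33% of the true change rests on an assumed active share of one third to two thirds and on a full plateau by week 12/8. With a partial effect at that visit the dilution is smaller, and with none it vanishes. The analysis is descriptive, and observed values and adverse events are untouched, so this is a correctable flaw in one safety summary. It does not undermine the safety evaluation as a whole.

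**What to change.** For rollovers from -30046 and -30060:

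1. In Sections 2.3.1, 9.7.1 and 9.7.2, define the reference for laboratory change as the parent-study pre-treatment baseline, as is already done for ECG. Apply it to all these patients without the footnote l switch. The SD-809-C-17 rollover keeps its own day 1 sample.
2. Keep change from day 1 as a secondary display, shown by parent-study arm so that on-drug and drug-free references are not pooled.
3. Reconcile Table 1 footnotes j and l with Sections 3.3 and 3.13.2, so that it is clear whether a laboratory sample is due at day 1 and which value carries that label.

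This concerns only the reference used in the analysis; the repeat test itself is not at issue. Leave the day 1 reference for vital signs, CDI-2 and TTS as it is.

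The cost is the change of wording, one extra table, and transfer of parent baseline laboratory data. The protocol already relies on parent baseline for ECG and for the TTS responder definition, but it does not say that pre-treatment laboratory values are transferred, so that should be confirmed. No new blood draw is needed.

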3.13.1. Procedures for Screening and Enrollment (Visit 1)

Informed consent/assent, depending on the child's age, as appropriate, will be obtained before any study procedures are performed. For patients rolling over from Study TV50717-CNS-30046 or Study TV50717-CNS-30060, informed consent/assent, as appropriate, may be obtained prior to the day 1 visit, up to 4 weeks in advance of open-label study participation.

For patients rolling over from Study TV50717-CNS-30046 or Study TV50717-CNS-30060, screening data will be obtained from the parent study (see [Table 1](#)). Informed consent/assent, as appropriate, must be given before any procedures related solely to Study TV50717-CNS-30047 are performed.

For patients from Study SD-809-C-17:

All screening procedures will be performed for patients rolling over from Study SD-809-C-17, as they will have been off IMP for several months at the time of enrollment into this study (TV50717-CNS-30047). A signed and dated informed consent form will be obtained from the parent/legally acceptable representative, and a signed and dated assent, depending on the child's age, as appropriate, will be obtained from each patient before any screening procedures commence, according to national laws and local IEC/IRB requirements. Parents/legally acceptable representatives will acknowledge and agree to the possible use of this information for the study by giving informed consent.

A patient who is screened but not enrolled may be rescreened 1 time if there is a change in the patient's medical background, a modification of study entry criteria, or other relevant change. (Note: Details of rescreening must be approved and documented by the medical monitor and/or CST team.)

The screening visit will take place not more than 31 days before the day 1 visit. The screening visit may be conducted over 2 separate visits at the discretion of the investigator. The following procedures will be performed at the screening visit for patients from Study SD-809-C-17:

- obtain written informed consent (and assent, depending on the child's age, as appropriate) before any other study-related procedures are performed
- conduct clinic visit
- review eligibility (inclusion and exclusion) criteria
- inform patients of study restrictions and compliance requirements
- review medical and psychiatric history
- review demographics information
- measure vital signs (pulse, BP, body temperature, and respiratory rate)
- perform full physical and neurological examinations (including height and weight; note: weight must be measured with shoes and outerwear off)
- perform 12-lead ECG (Note: ECG will be performed after at least 5 minutes rest in a supine or semi-supine position.).

- perform clinical laboratory tests, including serum chemistry, hematology, and urine analyses
- perform urine drug screen (UDS)
- perform a serum pregnancy (β -HCG) test (only in females who are postmenarchal or ≥ 12 years of age)
- administer the following questionnaires (Note: For MINI Kid and Children’s C-SSRS, children 13 years of age and under may be interviewed separately or jointly with the caregiver/adult as appropriate or defined by the scale. For children over 13 years of age, caregiver/adult involvement is strongly encouraged. Questions should be directed to the child, but the caregiver/adult should be encouraged to add relevant information. The YGTSS questionnaire should be performed before any blood draws or ECG assessments.):
 - MINI Kid (Note: The following modules will be used: Major Depressive Episode [Module A], [Hypo] Manic Episode [Module D], Obsessive-Compulsive Disorder [OCD; Module J], Alcohol Dependence/Abuse [Module L], Substance Dependence/Abuse [Non-alcohol; Module M], Attention Deficit Hyperactivity Disorder [ADHD; Module O], Conduct Disorder [Module P], and Psychotic Disorders and Mood Disorders with Psychotic Features [Module R].)
 - CDI-2, Parent and Self-Report Profiles (Note: Children 6 years of age on day 1 will not complete the Self-Report version; the caregiver/adult will complete the Parent version.)
 - C-SSRS (children’s baseline/screening)
 - YGTSS (Input from the caregiver/adult is required.)
- review medication history and concomitant medications
- inquire about adverse events

3.13.1.1. YGTSS Rater Certification

All investigators and subinvestigators who will be administering the YGTSS from screening through the end of study visit must undergo and pass a Rater Certification Program which will be provided separately from this protocol. Every effort must be made to ensure that the same certified rater administers the YGTSS to a specific patient at all visits where this scale is administered, especially at day 1 and at weeks 28, 30, and 54/early termination visits. However, if due to unforeseen circumstances the same rater is absolutely unavailable to complete a visit rating, the YGTSS can be administered only by another certified individual from that study site.

3.13.2. Procedures Before Investigational Medicinal Product Treatment (Day 1)

For patients rolling over from Study TV50717-CNS-30046 or Study TV50717-CNS-30060, the week 13 visit (Study TV50717-CNS-30046) or the week 9 visit (Study TV50717-CNS-30060) will be the day 1 visit for Study TV50717-CNS-30047. Patients rolling over from Study SD-809-C-17 will need to undergo all day 1 assessments. Day 1 assessments for

Study TV50717-CNS-30047 that are identical to Study TV50717-CNS-30046 week 13 or Study TV50717-CNS-30060 week 9 visit assessments do not need to be repeated.

The following procedures will be performed at the day 1 visit, as they:

- conduct clinic visit
- review eligibility (inclusion and exclusion) criteria (required for all patients)
- measure vital signs (orthostatic pulse and BP after standing for at least 3 minutes), height, and weight
- perform 12-lead ECG (required for all patients). Note: ECG will be performed after at least 5 minutes rest in a supine or semi-supine position.
- perform clinical laboratory tests, including serum chemistry, hematology, and urine analyses
- perform a urine pregnancy (β -HCG) test (required for all females who are postmenarchal or ≥ 12 years of age)
- administer the following questionnaires (Note: For C-SSRS, [REDACTED] and C&A-GTS-QOL, children 13 years of age and under may be interviewed separately or jointly with the caregiver/adult as appropriate or defined by the scale. For children over 13 years of age, caregiver/adult involvement is strongly encouraged. Questions should be directed to the child, but the caregiver/adult should be encouraged to add relevant information. The YGTSS, TS-CGI, [REDACTED] and TS-PGII questionnaires should be performed before any blood draws or ECG assessments.):
 - CDI-2, Parent and Self-Report Profiles (Note: Children 6 years of age on day 1 will not complete the Self-Report version; the caregiver/adult will complete the Parent version.)
 - C-SSRS (children’s SLV)
 - YGTSS; a complete assessment will be performed for patients who completed Study SD-809-C-17. For patients who completed Study TV50717-CNS-30046 or Study TV50717-CNS-30060, perform assessment of “Severity Ratings” of the questionnaire; inventory portions (ie, “Motor Tic Symptom Checklist” and “Phonic Tic Symptom Checklist”) do not need to be performed (Input from the caregiver/adult is required).
 - TS-CGI
 - TS-PGII (Input from the caregiver/adult is permitted.)
 - [REDACTED]
 - [REDACTED]
 - [REDACTED]

- 
- C&A-GTS-QOL (including VAS) (required for all patients)
 - dispense IMP (sufficient doses for 2 weeks [current dose level and next dose level] to cover the telephone contacts) and patient diary
 - patients will continue to enter dosing times in the diary through completion of the study
 - review concomitant medications
 - inquire about adverse events

A patient who is not enrolled in the study on the basis of results of day 1 assessments (eg, because inclusion and exclusion criteria were not met or enrollment did not occur within the specified time) may be rescreened if there is a change in the patient's medical background, a modification of study inclusion and exclusion criteria, or other relevant change. (Note: Details of rescreening must be approved and documented by the medical monitor and/or CST team.)

Patients from Study SD-809-C-17 who continue to meet the inclusion and exclusion criteria will be assigned a permanent unique treatment number. This assigned number will be entered in the CRF.

